## TRIAL PROTOCOL

**NCT NUMBER:** 03311646

**Document Date:** 7/24/2018

**MUSC IRB Protocol #:** Pro00069959

**Title:** Impact of exclusive use of low nicotine cigarettes on compensatory smoking

**Principal Investigator:** [name]

**NOTE:** Protocol is Version 6 and is the final approved IRB protocol. Two protocol changes are not reflected but were implemented for all study participants: 1) intervention order was fixed for all participants (NNC→VLNC) rather than counterbalanced, and 2) unblinding wording for participants was changed to either “All of the cigarettes provided to you and all other participants during this hotel stay have a normal nicotine content. The nicotine content is about the same as what would be available in a typical cigarette purchased on the market today” (NNC) or “All of the cigarettes provided to you and all other participants during this hotel stay have a very low nicotine content. The nicotine content is about 97% less than what would be available in a typical cigarette purchased on the market today” (VLNC).

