### **C7. Procedures**

Study participation consists of a screening visit and two four-night stays in the hotel.

**C7a. Screening visit.** After obtaining informed consent, screening assessments will be completed (measures described below). At the end of the session, eligible participants will be scheduled for two hotel stays. It will be stressed to participants that it is critical that they attend both hotel stays, and we have provided a completion bonus to maximize the likelihood of study completion. In our prior study (1), 100% of our participants completed the entire hotel protocol. A baseline puff topography assessment will be completed for eligible participants using participants’ usual brand cigarette. Puff topography provides an analysis of smoking behavior including changes in the rate or volume of inhalation which can influence smoke exposure and nicotine delivery of cigarettes.

**C7b. Hotel phase.** Participants will return to the lab on the morning of each hotel stay. Participants will complete a Timeline Follow Back Assessment about their tobacco use over the previous 14 days, and we will collect a first void urine for baseline assessment. We will also obtain an expired carbon monoxide sample.

Participants will arrive at the hotel and have their first opportunity to buy cigarettes at 4PM on Hotel Day 1. While at the hotel, participants will have “check in” times of 8AM, 12PM, 4PM, and 8PM. Check-ins will be used to collect physiological assessments, collect self-report questionnaires, and for participants to purchase more cigarettes if needed. Measures at the hotel are designed to assess the safety of the participants using the study product, the impact of nicotine reduction on physiological and behavioral measures of smoke exposure, and the impact of nicotine reduction on other key measures like withdrawal, craving, and reinforcement value. Participants will return all unused cigarettes and depart the hotel at 12PM on Hotel Day 5. Participants will spend approximately 96 hours (four 24-hr periods) in the hotel. A puff topography assessment will be completed each day by having participants smoke one of the research cigarettes through a device that measures how they smoke cigarettes. Puff topography provides an analysis of smoking behavior including changes in the rate or volume of inhalation which can influence smoke exposure and nicotine delivery of cigarettes.

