**The following questionnaires will be completed as an interview and entered into Redcap by study staff:**

1. Tobacco Use History Questionnaire: which measures variables such as smoking amount, cigarette brand, age of initiation, number of quit attempts, duration of quit attempts, and duration of smoking
2. Smoking Cessation Questionnaire to assess use of nicotine replacement therapy or smoking cessation medications to help participants quit smoking
3. Drug Use Questionnaire 12 + 1 month: measures drug use over the last 12 months and 1 month
4. Health Changes Questionnaire V1: assesses health changes since participant's last visit
5. Health Changes Questionnaire V2: assesses health changes since entering the hotel.
6. Timeline Followback: assesses tobacco use in the last two weeks.
7. Mini International Neuropsychiatric Interview (MINI) suicide subscale: to evaluate suicide risk
8. Brief Medical History: to assess current diagnoses, symptoms, and past health problems

9. Follow-up Call: Approximately 30 days after the end of the second hotel week, study staff will call each participant and complete a short follow-up call. During this call, we will assess current tobacco use and any quit attempts since the study ended. We will also ask participants whether they used any non-study tobacco products during their hotel stays. If participants self-report non-study tobacco use while at the hotel, we will ask about the frequency and rate of use, which products were used, and how participants obtained those products. Participants will be paid for the call regardless of whether they self-report non-study tobacco product use.

**The following questionnaires will be completed as an interview, tape recorded with the permission of the participants, and transcribed later:**

1. Qualitative Interview: In order to better understand participants' subjective experiences in the hotel and their opinions and reactions to a potential regulatory nicotine reduction policy, a 15-20 minute qualitative interview will be completed.

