**C13. Scientific rigor considerations**

Each participant will serve as their own control by completing a VLNC and NNC condition, in which all variables are held constant except the nicotine content of Spectrum cigarettes and the information that participants receive about nicotine content. Study staff will follow detailed protocols and scripts to standardize procedures. The order of conditions will be counterbalanced between the sets of 10 participants that complete the hotel stays together. Analyses will follow an a priori statistical analysis plan including rules for identifying

outliers and the use of a blinded third party for data cleaning as needed. Sample size was determined via a power analysis.

**C14. The National Institutes of Health now considers all ongoing clinical research to be in possession of a Certificate of Confidentiality.** With this certificate, the researchers cannot be forced to disclose information that may identify the participants, even by a court subpoena, in any federal, state, or local civil, criminal, administrative, legislative, or other proceedings. The researchers will use the Certificate to resist any demand for information that would identify the participants, except as explained below. The certificate cannot be used to resist a demand for information from personnel of the United States Government that is used for auditing or evaluation of federally funded projects or for information that must be disclosed in order to meet requirements of the Federal Food and Drug Administration. The Certificate of Confidentiality does not prevent the participant or a member of their family from voluntarily releasing information about themselves and their involvement in the research. If an insurer, employer, or other person obtains the participant's written consent to receive research information, then the researcher may not use the Certificate to withhold that information. The Certificate of Confidentiality does not prevent the researchers from disclosing voluntarily, without consent, information that would identify the individual as a participant of the research project in instances such as evidence of child abuse or a participant's threatened violence to self or others.

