- 5) **Smoking Study Cigarettes:** Smoking the study cigarettes could cause some minor adverse health effects such as headaches or experience withdrawal symptoms, which are listed below. Due to the altered nicotine levels, there could be a change in cigarette use including the manner in which smoke is inhaled. Participants may also experience increases in levels of carbon monoxide, a gas from smoke.
  - a. **Smoking Withdrawal:** Participants may experience smoking withdrawal symptoms during this study. These symptoms can include anger, irritability, frustration, anxiousness, nervousness, depressed mood or sadness, desire or craving to smoke, difficulty concentrating, increased appetite, hunger or weight gain, insomnia, problems sleeping or awakening at night, restlessness, impatience, constipation, dizziness, coughing, dreaming or nightmares, nausea, and sore throat. These feelings can be uncomfortable but are typically of minimal risk.
  - b. **Returning to Regular Smoking:** It is possible that if when participants return to smoking their usual brand of cigarette they may experience mild and transient nausea, dizziness, and lightheadedness.
  - c. **Changes in blood pressure and/or heart rate:** Smoking and nicotine can affect the cardiovascular system which may result in changes in blood pressure and/or heart rate.
  - d. **Changes in mood, emotions and psychiatric symptoms:** Smoking and nicotine can affect mood and emotions and are associated with psychiatric disorders including major depressive disorder, general anxiety disorder, bipolar disorder and eating disorders. Any changes in nicotine or cigarette consumption could adversely affect mood, emotions and the symptoms related to psychiatric conditions in some individuals.
  - e. **Smoking and medications:** Quitting smoking can greatly benefit participant health. However, changes in smoking rate can lead to changes in how well some medications work.

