### **Protection against risks.**

- 1) **Issues Related to Coercion:** The likelihood of this risk is low because the compensation is commensurate with the amount of time and effort required for this study. Participants will be compensated for their time at a rate that is commensurate with the time and effort required for this study (\$10/hr during the screening session, \$55/day during the hotel phase).
- 2) **Breach of Confidentiality:** The likelihood of breach of confidentiality is low as we will take precautions to minimize this risk. All data will be stored on a secure, password-protected server that is only available to research investigators.
- 3) **Risk of fire:** Participants will be advised not to smoke in bed or other unsafe areas.
- 4) **Smoking Cigarettes:** The study cigarettes have risks that are similar to conventional cigarettes, and all participants will be given information about smoking risks during the consent process and at the end of the study. Subjects will be encouraged to quit smoking and optimally all tobacco use at the end of study. We will perform a urine pregnancy test on female participants at the screening session and on the first day of each hotel week. Participants testing positive for pregnancy will be excluded (screening) or withdrawn (hotel phase). We will advise women to use proper birth control while enrolled in the study. Women who self-report using estrogen birth control will not be eligible to participate.
- 5) **Smoking Study Cigarettes:** Risks related to withdrawal are likely uncomfortable, but the risk is minimal. Although smoking the study cigarettes may result in increased smoking, we have observed in our prior studies that this increase is temporary, and smoking rates return to normal within 30 days after the study ends. This is true even for participants that experience large increases in smoke exposure during the study (>100% increase in CPD). We have established clear rules for monitoring and withdrawing participants (see Data and Safety Monitoring Plan). For example, participants would be withdrawn from the study if at any point, the average CO over two consecutive readings is greater than 99 ppm.

**If the subject decides to quit smoking before completing the entire study, this decision will be encouraged and supported. Subjects will be provided with a treatment manual and referral to available treatments.**

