### ***C. Monitoring and Withdrawal of Participants***

#### **Identifying Adverse Events**

While participating in the trial, adverse events and concomitant medications will be assessed at every lab visit and at the end of the Hotel Phase, and expired carbon monoxide will be obtained. Adverse events will typically be identified during the administration of the Health Changes Questionnaire, which will be administered at the end of the Hotel Phase,. Other events may be identified from physiological study measures or by spontaneous reports during non-scheduled assessments. [name] (CO-I) has worked closely with [name] (MD) in handling Adverse Events in the past, and [name] has agreed to be available as needed to discuss adverse events in this study.

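### With the order fixed as NNC then VLNC, no scheduled health question follows the VLNC stay in any participant

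*Combined protocol and SAP*

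**What the plan says.** **The risk.** Potential Risks (item 5b) and the Data Safety Monitoring Plan (section 6a, item 12) both warn about the return to usual-brand cigarettes: "It is possible that if when participants return to smoking their usual brand of cigarette they may experience mild and transient nausea, dizziness, and lightheadedness". Neither place links this to one of the two study cigarettes. The same lists say that changes in nicotine or cigarette consumption may worsen mood or psychiatric symptoms.

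**When health is asked about.** Under Identifying Adverse Events, "adverse events and concomitant medications will be assessed at every lab visit and at the end of the Hotel Phase". That section also allows for spontaneous reports. Among the interview questionnaires, Health Changes V1 looks back to the previous visit and V2 looks back only to hotel entry.

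**The contacts.** C7 states: "Study participation consists of a screening visit and two four-night stays in the hotel". C7b adds a lab visit on the morning of each stay. Interview item 9 adds a call about 30 days after the second hotel week, whose stated content is "During this call, we will assess current tobacco use and any quit attempts since the study ended", followed by questions on non-study tobacco products used in the hotel.

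**The order.** C13 plans that "The order of conditions will be counterbalanced between the sets of 10 participants that complete the hotel stays together". The cover note reports a change made for all participants: "intervention order was fixed for all participants (NNC→VLNC) rather than counterbalanced".

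**The concern.** A symptom that begins after discharge can be picked up actively only at a later contact that asks about health. For the first stay, that contact is the lab visit before the second. For the second stay there is none, because the 30-day call asks about tobacco only. Once VLNC became the last stay for everyone, the period after VLNC lost any scheduled health question, and the safety sections were not revised to match.

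At stake is what the trial can say about safety after VLNC discharge. With no active question, few or no reports of nausea, dizziness, lightheadedness or new mood change in that period could be read as evidence that they did not occur, when nobody was scheduled to ask.

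**Working it through.** The plan gives no figure on this point, so none can be reproduced. The check sets the scheduled contacts beside what each one can capture, then counts participants.

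**Step 1. What each contact can capture**

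| Contact | Source | Health asked? | Can it capture a symptom that starts after a stay? |
|---|---|---|---|
| Screening | C7a; Identifying Adverse Events | Yes | No, it precedes both stays |
| Lab, morning of stay 1 | C7b; Identifying Adverse Events | Yes | No, it precedes both stays |
| End of stay 1 | Interview item 5 (V2) | Yes, since hotel entry | No, the participant has not yet left |
| Lab, morning of stay 2 | C7b; interview item 4 (V1) | Yes, since last visit | Yes, after stay 1 |
| End of stay 2 | Interview item 5 (V2) | Yes, since hotel entry | No, the participant has not yet left |
| Call at about 30 days | Interview item 9 | No health item listed | No active question |

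The end of the Hotel Phase might mean the end of each stay or of both. On either reading, the assessment falls before the participant returns to the usual brand after stay 2, so the last column is unchanged.

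**Step 2. Count for 20 completers**

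The target is 20 completers (Power Analysis and Sample Size) in sets of 10 (C1), which gives 20 / 10 = 2 sets. Only a set that has VLNC first can meet a scheduled health question after VLNC.

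- Counterbalanced (C13): 1 set with VLNC first, 1 × 10 = 10 of 20.
- Fixed NNC then VLNC (cover note): 0 sets with VLNC first, 0 × 10 = 0 of 20.

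**Step 3. The same count by stay rather than by cigarette**

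- After the first stay: 20 of 20 are asked, under either order.
- After the last stay: 0 of 20 are asked, under either order.

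So the missing check after the last stay was always in the design. The order change moved that gap wholly onto VLNC.

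**Step 4. What other provisions cover**

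- Smoking level: Protection against Risks (item 5) relies on earlier experience that "smoking rates return to normal within 30 days after the study ends". The call at about 30 days asks about current tobacco use, so this expectation has a scheduled check.
- Events identified in the hotel: Management of SAEs and Other Study Risks has participants with an adverse event followed until it resolves, stabilises or is clearly unrelated.
- Symptoms that begin after VLNC discharge: neither provision reaches them, which leaves spontaneous reports.

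**The case against.** A reader might infer that the named risk goes unmonitored in every participant, that the order change created the gap, and that it leaves a 30-day window unwatched. The documents do not support any of these.

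- The return-to-usual-brand risk is not tied to VLNC. That it would be greater after VLNC is an inference from the contents in C1 (0.4 against 15.8 mg/g). As written, the risk is checked once in everyone, at the lab visit after the NNC stay.
- The last stay lacked a later check under either order, and counterbalancing would still have left 10 of 20 without one after VLNC.
- The 30 days refers to smoking rates, which the call assesses. No section gives the symptoms a 30-day window.
- Spontaneous reports remain a route, so the accurate description is that no active question is scheduled.
- A participant withdrawn for an adverse event, including a high carbon monoxide reading, is promised medical follow-up. The second hotel week can also be read as a group calendar date, so the missing call date mainly concerns people who leave early for other reasons, and there it is an ambiguity.

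Two further objections have weight. Recall at 30 days suits mild, transient symptoms poorly. And the public text breaks off between C7c and the questionnaire list, where a schedule of assessments may have stood.

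All of this limits the size of the point. It does not supply a health question after the VLNC stay: C7, interview item 9 and Identifying Adverse Events agree with one another that there is none.

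**Conclusion.** The point holds in a limited form. Under the implemented order, 0 of 20 completers have a scheduled health question after the VLNC stay, against 10 of 20 under the order in C13. New symptoms after that discharge, including the named symptoms and any mood change, depend on spontaneous reports.

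Its importance is modest. It concerns how completely safety events are collected and leaves the primary outcomes, the analysis and the power untouched. It rests on three assumptions: that the 20 completers come in two sets of 10; that the call contains only what interview item 9 lists; and that no assessment schedule in the part of the protocol not visible adds a health item to the call or a later visit.

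**What to change.** 1. In interview item 9, add the existing Health Changes question to the 30-day call, with the reference period set to the time since leaving the hotel. Complete the Adverse Event Form on a positive answer, as the Data Safety Monitoring Plan already does for that questionnaire.
2. Time the call from each participant's last hotel stay, so that those who leave early also have a date.
3. Revise Identifying Adverse Events to list the call, and reconcile C13 with the order in the cover note.

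The cost is a few minutes on about 20 calls that are already planned and paid for, plus a minor amendment. The drawback is that mild, transient symptoms will be under-recalled at 30 days, so the answers would be incomplete.

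The cover note says that the fixed order was used for all participants, so the calls may be finished. If so, the report should state that health events after the final (VLNC) stay were not systematically collected, so that absence of reports is not taken as absence of events. That costs one sentence.

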**The following physiological measures will be entered into Redcap by study staff:**

1. Urine Pregnancy Test (HCG detection): will be performed for female participants with childbearing potential.
2. Urine Drug Screen: will be performed to assess for the presence of illicit drugs including marijuana, cocaine, opiates, benzodiazepines, barbituates, amphetamines, methadone, methamphetamines, tricyclic antidepressants, and PCP (positive test for marijuana or tricyclic antidepressants acceptable).
3. Expired Carbon Monoxide (CO) levels will be assessed using a Smokerlyzer Micro + CO meter (Bedfont Instruments), a reliable and valid measure of recent smoking. Two carbon monoxide samples will be collected at each sample, and if the two samples differ by more than two ppm, a third sample will be collected. The final CO outcome will be the average of the two (or three) samples.
  - a. Nic Alert Strips: will be used to assess cotinine levels if a participant's carbon monoxide reading is less than or equal to 8.
4. First Void Urine: A urine sample participants collect of their first void urine from that morning using a urine collection cup provided by the lab. This urine will be stored at the Clinical Neuroscience Laboratory at MUSC and shipped to the Centers for Disease Control for testing of exposure to tobacco and tobacco smoke. Samples sent to the CDC will be coded, and the key linking codes to identifying information will remain at MUSC. The CDC will destroy any residual samples once analyses are complete.
5. 24-hour Urine: Participants will collect all urine in the hotel using collection containers provided by the lab. Participants will return their urine and receive a new container every 24 hours. This urine will be stored at the Clinical Neuroscience Laboratory at MUSC and shipped to the Centers for Disease Control for testing of exposure to tobacco and tobacco smoke. Samples sent to the CDC will be coded, and the key linking codes to identifying information will remain at MUSC. The CDC will destroy any residual samples once analyses are complete.

**Opportunity to purchase cigarettes:** Participants will have the opportunity to "purchase" cigarettes from hotel staff at each check in.

**Cigarette Butt Collection:** Participants will be provided with a plastic bag in which to collect their cigarette butts. Participants will return their bag and receive new bags every 24-hrs. The first butt of each week and the first butt of each day will be kept separate.

**Puff Topography:** Participants will complete a puff topography assessment in which they smoke a cigarette through a CReSS device that provides an analysis of smoking behavior including changes in the rate or volume of inhalation which can influence smoke exposure and nicotine delivery in cigarettes.

